3.1.5 Summary Statistics

Categorical data will generally be summarized with counts and percentages of subjects. The denominator used for the percentage calculation will be clearly defined. Continuous data will generally be summarized with descriptive statistics including n (number of non-missing values), mean, median, 25th and 75th percentiles, standard deviation, minimum, maximum and 95% confidence intervals where appropriate.

3.1.6 Hypothesis Testing

To demonstrate the treatment effect of SLN360 compared with placebo, the following hypothesis:

$$H_0: \mu_T = \mu_P$$

will, at the 5% significance level, be tested against the alternative hypothesis:

$$H_1: \mu_T > \mu_P$$

wherein μ denotes the mean time-averaged change in Lp(a) from Day 1 pre-dose to Week 36, T denotes SLN360 and P denotes placebo. For estimating treatment effects, the difference between treatments and corresponding confidence intervals will be provided.

No formal statistical hypothesis testing is planned for safety data.

3.1.7 Evaluation of Site Effect

It is not planned to perform a subgroup analysis on individual or groups of centres.

3.1.8 Handling of Dropouts and Missing Data

Missing data will not be imputed unless otherwise specified. Only observed data will be used in the summaries and analyses.

In all listings, missing or incomplete dates should be left as they have been recorded. However, for calculation / sorting / assignation based on dates, the following methods will be used:

- 1) The most conservative approach will be systematically considered (i.e. if the onset date of an AE is missing / incomplete, it is assumed to have occurred during the active phase (i.e. a TEAE for AEs) except if the partial onset date or other data [stop date, ...] indicates differently).
- 2) A missing/incomplete date of medical history or disease diagnosis will be assumed to have occurred before any study treatment.
- 3) If a partial date and the associated information do not allow to state about the assignation to a group / category, all the possible groups / categories will be considered (i.e. an AE could be assigned to several possible doses at event onset according to its partial onset date and stop date. Particularly an AE with missing start date will be assigned to each dose received before its end date.).
- 4) Where this is possible, the derivations based on a partial date will be presented as superior inequalities (i.e.: for an AE started in FEB2004 after the administration performed on 31JAN2004, the days since last dose will be “ ≥ 2 ”, similarly the duration of ongoing AEs or medication will be “ $\geq xx$ ” according to the start and last visit dates).

3.2 Analysis Populations

3.2.1 Screened Population

Screened Population includes all participants who signed an informed consent form (ICF).

3.2.2 Safety Population

Safety Population includes all participants who received at least one dose of study drug.

3.2.3 Pharmacodynamic Population

Pharmacodynamic Population includes all participants who received at least one dose of study drug and have evaluable PD data.

3.3 Subject Data and Study Conduct

3.3.1 Subject Disposition

Counts and percentages of subjects who were screened (signed informed consent), discontinued early during screening (screen failures), and randomized will be summarized in total based on all screened subjects. Reasons for early discontinuation will also be summarized.

Counts and percentages of subjects who were randomized, discontinued treatment early, completed study treatment, discontinued early from the study, and completed the study will be summarized by treatment and in total based on all randomized subjects. Primary reasons for early discontinuation treatment and study will also be summarized. Early discontinuation treatment and study due to Coronavirus disease 2019 (COVID-19) will be summarized.

3.3.2 Protocol Deviations

Counts and percentages of subjects with protocol deviations by deviation category will be summarized by treatment and in total based on all randomized subjects. Protocol deviations related to COVID-19 will be summarized in the same manner.

3.3.3 Analysis Populations

Counts and percentages of subjects in each analysis population will be summarized by treatment and in total based on all randomized subjects. Reasons for exclusion from each analysis population will also be summarized.

3.3.4 Demographic and Baseline Characteristics

The following demographic and baseline characteristics will be summarized:

- Age (years) and age categories (18-64 years, ≥ 65 years)
- Sex (male, female)
- Childbearing potential (yes, no)
- Race (American Indian or Alaska Native, Asian, Black or African American, Native Hawaiian or Other Pacific Islander, White, other)
- Ethnicity (Hispanic or Latino, Not Hispanic or Latino, not reported, unknown)
- Height (cm)
- Weight (kg)
- Body mass index (BMI) (kg/m^2)
- Time from the initial date of elevated Lp(a) to randomization date (months)

Demographic and baseline characteristics will be summarized with descriptive statistics or counts and percentages of subjects as appropriate by treatment and in total for the Safety Population.

3.3.5 Medical History

Medical history will be coded to system organ class and preferred term using the Medical Dictionary for Regulatory Activities (MedDRA). Counts and percentages of subjects with medical history by system organ class and preferred term will be summarized by treatment and in total based on the Safety Population.

Counts and percentages of subjects with high-risk conditions for ASCVD will be summarized by treatment and in total based on the Safety Population.

3.3.6 Concomitant Medications

Prior and concomitant medications will be coded to anatomical therapeutic chemical (ATC) class and preferred term using the WHO Drug Dictionary. For summary purposes, medications will be considered prior medications if they stopped prior to the first dose of study drug and concomitant medications if they were taken at any time after the first dose of study drug (i.e., started prior to the first dose of study drug and were ongoing or started after the first dose of study drug).

If a medication has a missing start date, the most conservative approach will be applied and the medication start date will be assumed to be during the active phase unless other data (e.g. stop date) indicates differently. For a missing stop date, the medication will be assumed to be ongoing.

If a medication has incomplete start or stop dates, dates will be imputed to determine whether a medication should be considered prior or concomitant. If a medication start date is incomplete, the first

day of the month will be imputed for missing day and January will be imputed for missing month. If a medication stop date is incomplete, the last day of the month will be imputed for missing day and December will be imputed for missing month. Incomplete start and stop dates will be listed as collected without imputation.

Counts and percentages of subjects taking prior and concomitant medications by ATC class and preferred term will be summarised by treatment and in total based on the Safety Population.

3.3.7 Study Drug Exposure and Compliance

Total dose administered (mg), total planned and actual volume administered (mL), number of doses and duration of exposure will be included in an overall summary by treatment based on the Safety Population with descriptive statistics.

Duration (weeks) = (Date of last injection- Date of first injection +1))/7.

For each dose, whether full dose was administered plus reason for not administering the full dose and number of injections will be summarized by treatment based on the Safety Population with descriptive statistics.

All information collected on the eCRF related to study treatment will be listed.

3.4 Efficacy Assessment

Efficacy data will be summarized by randomized treatment based on Pharmacodynamic Population.

3.4.1 Primary Endpoint

Primary Estimand

The primary estimand for this study is defined by the following attributes:

- Target population: participants with elevated Lp(a) at high risk of ASCVD events
- Treatments: SLN360 versus placebo
- Primary outcome measure: time-averaged percent change in Lp(a) molar concentration from Day 1 pre-dose to Week 36
- Analysis population: Pharmacodynamic Population
- Intercurrent events: prohibited medications/procedures and permitted medications (defined in protocol section 9.2 and 9.3), death, early withdrawal from study drug, and early withdrawal from the study.
- Analysis set and handling of intercurrent events: Treatment policy strategy will be used. All values of Lp(a) from scheduled assessments up to Week 36 will be included in the calculation of time-averaged percent change for each participant
- Population level summary: difference in mean time-averaged percent change in Lp(a) from Day 1 pre-dose to Week 36 between treatment groups

Time-averaged percent change from Week 4 to Week 36 is calculated from Week 4 corrected area under the curve (AUC) using linear trapezoidal method from Week 4 to Week 36 divided by the per-patient total time interval. Note that the Day 1 pre -dose values will be excluded from the time-averaged calculations (i.e., for each participant, the initial value included in the calculation will be from their first scheduled post-baseline assessment). Furthermore, the actual analysis day of each assessment will be used in the AUC calculation.

If the last available measurement of Lp(a) is before Week 36, time-averaged percent change in Lp(a) from Day 1 pre-dose to Week 36 will be calculated by arithmetic mean of all percent changes in Lp(a) from Day 1 pre-dose up to the last available time point before Week 36.

Analysis of variance will be used to test for differences between each active treatment group (i.e., Group 3, 4, or 5 in Table 1) and the pooled placebo groups (i.e., Groups 1 and 2 in Table 1 combined) for time-averaged percent change in Lp(a). Time-averaged percent change from Day 1 pre-dose to Week 36 in Lp(a) will be the dependent variable and treatment will be included as a factor. The least squares means, standard errors, and 2-sided 95% confidence intervals for each treatment group and for the pairwise comparisons between the SLN360 and placebo groups will be provided.

Holm's procedure will be used to control multiplicity of pairwise comparisons between each SLN360 group and the pooled placebo group. p-values will be first ordered from the smallest to the largest. $p_{(1)}$ represents the smallest value, $p_{(2)}$ the next-smallest p-value, $p_{(3)}$ the third-smallest p-value.

- (1) The test begins by comparing the smallest p-value, $p_{(1)}$, to 0.05/3 or 0.0167. If this $p_{(1)}$ is less than 0.0167, the pairwise treatment comparison with this p-value is considered significant.
- (2) The test then compares the next-smallest p-value, $p_{(2)}$, to 0.05/2 or 0.025. If this $p_{(2)}$ is less than 0.025, the pairwise treatment comparison with this p-value is also considered significant.
- (3) The test then compares the next ordered p-value, $p_{(3)}$, to 0.05. If this $p_{(3)}$ is less than 0.05, the pairwise treatment comparison with this p-value is also considered significant.

Pairwise comparisons between SLN360 groups will be provided and considered exploratory and multiplicity adjustments will not be applied.

P-values below 0.05 will still be considered nominally significant.

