2.3 Study Endpoints

2.3.1 Primary Endpoint

The primary endpoint is the time-averaged percent change in Lp(a) molar concentration from baseline to Week 36.

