2.3.2.2 Pharmacodynamics and Efficacy

The secondary pharmacodynamic (PD) and efficacy endpoints are:

- Time-averaged percent change in Lp(a) molar concentration from baseline to Week 48 and Week 60.
- Time-averaged absolute change in Lp(a) molar concentration from baseline to Week 36, Week 48, and Week 60.
- Time-averaged percent and absolute change in Lp(a) mass concentration, ApoB, LDL-C, HDL-C, total cholesterol and triglycerides, from baseline to Week 36, Week 48, and Week 60.
- Percent and absolute change in Lp(a) molar concentration, Lp(a) mass concentration, ApoB, LDL-C, HDL-C, total cholesterol, triglycerides, oxidized phospholipids, and C-reactive protein, from baseline by visit (i.e., not time-averaged)

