3.1.2 Analysis Visits

For pharmacodynamics and efficacy parameters, visits will be assigned to analysis visits according to the following visit windows. Within each analysis visit window, scheduled visits will be assigned to analysis visits as recorded on the case report form (CRF). If no scheduled visit is within the analysis visit window, measurement(s) taken at a visit close to the target analysis day will be used as the measurement for that specific visit. Unscheduled visits will not be used unless the scheduled result has not been reported. If samples are collected after the scheduled week 60 analysis these will not be included.

Analysis Visit	Target Analysis Day	Low Analysis Day	High Analysis Day
Screening			
Baseline	1		1
Week 1	8	2	19
Week 4	29	20	43
Week 8	57	44	71
Week 12	85	72	99
Week 16	113	100	127
Week 20	141	128	155
Week 24	169	156	183
Week 28	197	184	211
Week 32	225	212	238
Week 36	252	239	267
Week 40	281	268	309
Week 48	337	310	379
Week 60	421	380	

No study visit window will be used for safety parameters. Analysis visits will be based on the nominal visits as captured on the CRFs.

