3.4.2 Secondary Pharmacodynamics and Efficacy Endpoints

Time averaged secondary endpoints will be calculated and analyzed using the same conventions as the primary endpoint.

For each PD parameter, percent and absolute change from Day 1 pre-dose to each visit will be summarized descriptively. The least squares means, standard errors, and 2-sided 95% confidence intervals from analysis of variance will be provided for each treatment group and for the pairwise comparisons of each SLN360 group and placebo. Figures displaying mean (+/- standard deviation) by visit will be plotted for Lp(a), Apolipoprotein B, LDL Cholesterol, HDL Cholesterol, Total Cholesterol, Triglycerides, Oxidized Phospholipids, and C Reactive Protein will be displayed at baseline and each post-baseline visit. Additionally, figures for mean change and percent change (+/- standard deviation) from baseline will be presented for Lp(a), Apolipoprotein B, LDL Cholesterol, and C Reactive Protein will be displayed for each post-baseline visit.

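### SAP 3.4.1 gives conflicting averaging windows for the primary endpoint (Week 4 start versus first post-baseline visit, Week 1), leaves its Week 4 correction undefined and weights early leavers differently

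*SAP*

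**What the plan says.** SAP 2.3.1 states: "The primary endpoint is the time-averaged percent change in Lp(a) molar concentration from baseline to Week 36". The estimand and the analysis-of-variance sentence in SAP 3.4.1 use the equivalent label, Day 1 pre-dose to Week 36.

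SAP 3.4.1 then gives these rules for computing the variable:

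- **Formula.** "Time-averaged percent change from Week 4 to Week 36 is calculated from Week 4 corrected area under the curve (AUC) using linear trapezoidal method", with the area divided by each participant's own time interval.
- **First value.** The Day 1 value is left out of the average, and "the initial value included in the calculation will be from their first scheduled post-baseline assessment".
- **Values included.** The estimand bullet on intercurrent events says: "All values of Lp(a) from scheduled assessments up to Week 36 will be included in the calculation of time-averaged percent change for each participant".
- **Last value before Week 36.** The result is instead "calculated by arithmetic mean of all percent changes in Lp(a) from Day 1 pre-dose up to the last available time point before Week 36".

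SAP 3.1.2 says: "For pharmacodynamics and efficacy parameters, visits will be assigned to analysis visits according to the following visit windows". The table beneath that sentence lists Week 1 (target Day 8) as the first post-baseline visit and Week 4 (target Day 29) as the second.

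The secondary endpoints in SAP 2.3.2.2 include "Time-averaged percent change in Lp(a) molar concentration from baseline to Week 48 and Week 60", and SAP 3.4.2 adds: "Time averaged secondary endpoints will be calculated and analyzed using the same conventions as the primary endpoint". SAP section 6 declares no change from the protocol.

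**The concern.** A Day 1 pre-dose reference for percent change can coexist with an average that starts later, so the label and the formula do not conflict on the reference value. They conflict on where averaging starts. The formula excludes Week 1. The next sentence, read with the visit table, includes it. So does the estimand bullet, and so does Protocol 12.2.1, which takes in every available Lp(a) value.

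The Week 4 correction appears once, without a definition, and does not fit a Day 1 reference. The rule for early leavers changes both the window and the weighting.

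The trial's stated aim is to characterise magnitude and duration of Lp(a) lowering across regimens (Protocol 1.2), and Protocol 8.2.1 sets a programme objective of roughly 80% lowering. The size of the estimate is therefore a main result. If the window is settled after unblinding, it becomes a post hoc choice on the primary endpoint. SAP 3.4.2 carries the same ambiguity to the time-averaged secondary endpoints at Weeks 36, 48 and 60.

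**Working it through.** **1. The plan's own figure.** SAP 2.2.4 claims about 90% power with 10 per arm for a 60-point difference and SD 40. The standardised difference is 60 / (40 × √(2/10)) = 3.354. At two-sided 5%, the normal approximation gives 91.8% and the noncentral t gives 88.7%. The figure reproduces.

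**2. Windows, from the SAP target days (8, 29, 57, 85, 113, 141, 169, 197, 225, 252).**

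| Start | Length (days) | Left out by a Week 4 start |
|---|---|---|
| Week 4 | 252 − 29 = 223 | – |
| Week 1 | 252 − 8 = 244 | 21 |
| Day 1 | 252 − 1 = 251 | 28 |

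**3. Effect on a participant with a Week 36 value.** Let a1 and a4 be the percent changes at Weeks 1 and 4, and M the trapezoid mean over Days 29 to 252.

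- Week 4 start: M
- Week 1 start: [21(a1 + a4)/2 + 223M] / 244
- Day 1 start, with 0% at Day 1: [7a1/2 + 21(a1 + a4)/2 + 223M] / 251

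Example with assumed values a1 = −40 and −85 from Week 4 on:

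- Week 4 start: −85.0
- Week 1 start: (−1312.5 − 18955) / 244 = −83.1
- Day 1 start: (−140 − 1312.5 − 18955) / 251 = −81.3

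The assumed grid is a1 from −20 to −60, and a4 and M each from −70 to −95. Compared with a Week 1 start, the Week 4 reduction differs by:

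- at one end, 21 × (−77.5 + 70) / 244 = −0.6 points (smaller);
- at the other, 21 × (−45 + 95) / 244 = 4.3 points (larger).

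Compared with a Day 1 start, it is larger by 122.5/251 = 0.5 to 1645/251 = 6.6 points.

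Full visit-by-visit profiles, also assumed (Week 1 from −10 to −70, Week 4 at −80, later visits −62 to −94), give a gap between the Week 4 and Week 1 starts of 0.6 to 3.8 points.

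**4. The undefined correction.** If it meant subtracting the Week 4 value, the example would give −85 − (−85) = 0, which is not a change from baseline.

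**5. Early leavers.** The share of the average carried by Week 1 needs no assumed data:

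| Last value | Arithmetic mean | Week 1 trapezoid | Week 4 trapezoid |
|---|---|---|---|
| Week 32 | 1/9 = 11.1% | 10.5/217 = 4.8% | 0% |
| Week 16 | 1/5 = 20% | 10.5/105 = 10% | 0% |

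In the example, the arithmetic mean is (−40 − 8 × 85)/9 = −80.0 with last value at Week 32 and (−40 − 4 × 85)/5 = −76.0 at Week 16. A Week 4 trapezoid gives −85.0 in both cases. The switch of method is also unnecessary. The area is already divided by the participant's own interval, so it can be computed for anyone with two values in the window.

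**6. Power.** With 40 against 40 (one active group against pooled placebo), SD 40 and the strictest Holm level of 0.05/3, noncentral t power exceeds 0.999 for a difference of 60 points and also for 54.

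**The case against.** The strongest reply is that the text has a Week 4 reading. The sentence on the first post-baseline value may only explain that Day 1 is dropped from the Week 4 to Week 36 calculation just described. The estimand bullet may only serve to keep values after withdrawal or prohibited medication. That intent is plausible. But neither sentence limits itself to Week 4 onward, and as written both take in Week 1.

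Protocol 6.4 says that not every parameter may be measured at every visit. If Lp(a) is not assayed at Week 1, the two starts coincide. This limit stands. The SAP does not say so, however, and it gives the efficacy parameters a Week 1 window.

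The upper ends of the ranges come from an extreme corner. A Week 4 value of −70 with a Week 4 to 36 mean of −95 needs later visits to average about −97, while Protocol 1.1.3.3 reports a maximal median change of −98% at 600 mg, a dose not used here. This is fair. The worked example gives gaps of 1.9 points (Week 1) and 3.7 points (Day 1).

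Comparison of Groups 3 and 4 is little affected. Both receive the same dose at Week 0 and diverge only after Week 16, so a Week 1 start multiplies their difference by 223/244, or about 0.91. The early-leaver effect on an arm mean is also modest. If 5% to 15% of an arm were affected (an assumption), gaps of 5 to 9 points per person would move the mean by about 0.3 to 1.4 points.

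Finally, the protocol leaves derivation algorithms to the SAP, and SAP section 7 leaves programming detail to another document. That document may settle the code, but it does not remove a contradiction in the SAP.

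**Conclusion.** The concern holds. The SAP states conflicting rules for one primary variable, so the primary estimate cannot be reproduced from the SAP alone. The choice of start moves the estimated reduction by a few points: −0.6 to 4.3 between Week 4 and Week 1, and 0.5 to 6.6 between Week 4 and Day 1. These ranges rest on assumed percent changes and on Lp(a) being measured at Week 1. The window lengths and early-leaver weights rest only on the SAP's target days.

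A Week 4 start would also not match the baseline-to-Week-36 label, because it leaves out the 28-day onset period. The conclusion against placebo is safe. Because the conflict concerns the primary endpoint's definition, it should be resolved before unblinding.

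**What to change.** Amend the SAP before unblinding:

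1. Delete the Week 4 correction and state that percent change is always relative to the Day 1 pre-dose baseline.
2. State one averaging window and one trapezoid formula on actual days. A start at the first scheduled post-baseline visit (Week 1) fits most of the current wording. A Day 1 start at 0% is also coherent if the exclusion sentence is changed. If Week 4 is intended, rename the endpoint as Weeks 4 to 36 (and likewise to Weeks 48 and 60) in SAP 2.3.1, 2.3.2.2, 3.1.6 and 3.4.1, and align the sentences on the first value and on values included.
3. For participants whose last value precedes Week 36, use the same start and trapezoid up to that value, divided by their own elapsed days. If only one value lies within the chosen window, use it. State what happens when there is none, and when Week 36 is missed but a later value exists.
4. Record any departure from the protocol endpoint in SAP section 6.
5. State whether Lp(a) is assayed at Week 1.

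The cost is SAP wording only. Compared with a Week 4 start, a Week 1 start may report a reduction up to about 4 points smaller, and a Day 1 start up to about 7 points smaller, on the assumed grid. Keeping Week 4 and renaming changes no value for participants with a Week 36 measurement.

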12.2. Estimands

12.2.1. Primary Estimand

The primary estimand for this study is defined by the following attributes:

- Target population: participants with elevated Lp(a) at high risk of ASCVD events
- Treatments: SLN360 versus placebo
- Primary outcome measure: time-averaged change in Lp(a) from baseline to Week 36
- Analysis set and handling of intercurrent events: All available values of Lp(a) will be included in the calculation of time-averaged change from baseline in Lp(a)
- Population level summary: difference in mean time-averaged change in Lp(a) from baseline to Week 36 between treatment groups

Study Number: SLN360-002	Compound No.: SLN360
Protocol	Version: 1.0

Further details will be included in the SAP.

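### SAP 3.4.1 gives two start points for the primary time average, and scores participants whose last Lp(a) is before Week 36 by a different, unweighted formula (minor)

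*SAP*

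**What the plan says.** All of the following is in SAP 3.4.1 unless stated.

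- **AUC.** The time average is computed "using linear trapezoidal method from Week 4 to Week 36 divided by the per-patient total time interval".
- **First value.** Day 1 pre-dose is excluded, and "the initial value included in the calculation will be from their first scheduled post-baseline assessment". In the SAP 3.1.2 visit table that assessment is Week 1 (target Day 8); Week 4 (Day 29) is the second.
- **Values included.** "All values of Lp(a) from scheduled assessments up to Week 36 will be included in the calculation of time-averaged percent change for each participant". The outcome itself is named as running from Day 1 pre-dose to Week 36.
- **Early leavers.** "If the last available measurement of Lp(a) is before Week 36", the AUC is dropped and the score is "calculated by arithmetic mean of all percent changes in Lp(a) from Day 1 pre-dose up to the last available time point before Week 36".
- **Estimand.** "Treatment policy strategy will be used". The listed intercurrent events include "death, early withdrawal from study drug, and early withdrawal from the study".
- **Analysis.** One ANOVA with treatment as the factor compares each active group with pooled placebo, under Holm's procedure. Comparisons between active groups are exploratory.

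SAP 3.4.2 applies the same conventions to the time-averaged secondary endpoints, which SAP 2.3.2.2 sets at Weeks 36, 48 and 60. SAP 3.1.8 imputes nothing unless another rule is specified; the leaver mean is such a rule.

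**The concern.** Two careful programmers could derive different primary endpoints for every completer. A Week 4 start drops a scheduled value that two other sentences in the same section require. The sentence on the first value cannot be read only as excluding Day 1, because it goes on to name the visit at which the calculation begins.

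The leaver rule is a second estimator. It has no time weighting, covers a shorter span and, taken literally, counts Week 1. Week 1 is not typical of later visits: Protocol 1.1.3.3 puts the greatest change between 30 and 60 days after dosing. Yet the result enters the ANOVA as an average to Week 36, alongside the completers' AUC.

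There is also an estimand mismatch, limited to some participants. For those who stop drug but keep attending, using every value fits treatment policy. For those who leave the study, a mean that stops at the last visit is closer to a while-on-study average. The SAP does not say how the span after death is scored.

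At stake are the reported time averages and the exploratory comparisons between regimens. These matter because the Protocol's stated aim (1.2) is to characterise regimens by magnitude and duration of Lp(a) lowering.

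**Working it through.** **1. The plan's own power figure.** Inputs from SAP 2.2.4: difference 60, SD 40, 10 per arm, 5% level (two-sided, as the intervals are). The standardised difference is 60 / (40 × √(2/10)) = 3.354, and Φ(3.354 − 1.960) = 91.8%. The noncentral t version gives 88.7%. The stated figure of approximately 90% is reproduced.

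**2. Weight of Week 1, from the visit days alone.** SAP 3.1.2 target days to Week 36 are 8, 29, 57, 85, 113, 141, 169, 197, 225 and 252.

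- Completer, Week 4 start: 0.
- Completer, Week 1 start: [(29 − 8)/2] / (252 − 8) = 10.5/244 = 4.3%.
- Leaver, mean of k visits: 1/k.

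| Last visit | Visits in mean | Week 1 weight in the mean | Week 1 weight in a Week 1-start trapezoid over the same span |
|---|---|---|---|
| Week 4 | 2 | 50% | 50% |
| Week 8 | 3 | 33% | 21% |
| Week 16 | 5 | 20% | 10% |
| Week 32 | 9 | 11% | 4.8% |

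**3. Two simple illustrations (assumed values).** Take −40% at Week 1 and a constant −85% from Week 4.

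- Completer: −85.0% from Week 4; −85 + 0.043 × 45 = −83.1% from Week 1.
- Last seen at Week 8: (−40 − 85 − 85)/3 = −70.0%.
- Last seen at Week 32: (−40 − 8 × 85)/9 = −80.0%.

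Now take a profile resembling 24-week dosing: −40 at Week 1, then −85, −90, −85, −77, −65, −55, −88, −90, −86. The Week 4 to 36 AUC is −79.4%. Someone last seen at Week 8 scores −71.7% under the mean, but −87.5% under a Week 4-start AUC cut at Week 8. Counting Week 1 and stopping early therefore push in opposite directions.

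**4. Size at arm level (modelled).** The documents give no individual profiles and no dropout rate, so both are assumed.

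- Model: dR/dt = kout(1 − I − R), I = 0.99·C/(C50 + C), C = Σ dose × exp(−k × time since dose); dose 1.0 for 300 mg and 1.5 for 450 mg; placebo flat.
- Nine profiles: Lp(a) half-life 5, 7 or 9 days, crossed with a single-dose 300 mg nadir of −85, −90 or −95%.
- C50 and k are solved to give −60% at Day 150 (Protocol 12.3.1) or, alternatively, −70%.
- Leaving: 10%, spread evenly over last visits at Weeks 8 to 32.
- Leaver score: mean of all visits from Week 1 to the last. Comparators: the Week 4 to 36 trapezoid with all doses (completer course), or with doses after the last visit removed (doses received).

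| Week 36, percentage points, across the three active arms | −60% at Day 150 | −70% at Day 150 |
|---|---|---|
| Completers: reduction lost by starting at Week 1 | 0.4 to 2.4 | 0.7 to 2.5 |
| Arm mean, leaver rule v. completer course | understated by 0.1 to 1.0 | understated by about 0.3 to 1 |
| Arm mean, leaver rule v. doses received | 1.1 too favourable to 0.2 understated | both signs in every arm, within about 0.75 either way |
| One leaver last seen before the second dose, v. doses received | 2.5 to 24.5 too favourable | about 17 too favourable to 6.5 understated |

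Arm shifts scale with the leaving rate. A 1.1-point shift at 10% becomes 1.1 × 0.5 = about 0.6 at 5%, and 1.1 × 2 = 2.2 at 20%.

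**5. Scale.** The standard error of an arm mean is 40/√40 = 6.3 points. For the placebo test, 40 v. 40 at the first Holm step (0.05/3 = 0.0167), the standardised difference is 60 / (40 × √(2/40)) = 6.71, and power is above 99.9%.

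**6. Weeks 48 and 60.** The last two intervals are 8 weeks (Week 40 to 48) and 12 weeks (Week 48 to 60), so an unweighted mean departs further from a time average there.

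**The case against.** The strongest reply is that the effects are small, no confirmatory test changes, and regimen comparisons are exploratory. That stands, and it is why the point is minor.

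Second, if the Week 4 start also governs the mean, little is left for late leavers: at most 0.6 points for someone last seen at Week 32, under the −60% calibration. That stands too, but the SAP does not say so, and its wording for the mean covers all changes from Day 1.

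Third, few people may be affected. Protocol 10.2.3 asks that participants withdrawn from treatment return at Week 36 and end of study if they cannot attend other visits. A missed Week 36 followed by a later value does not trigger the rule. Both points hold. The early-withdrawal assessment in Protocol 10.2.2 does not help in the same way: held before Week 36, it still leaves the last Lp(a) before Week 36.

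Fourth, a replacement is not automatically better. Giving leavers the completer course (plain missing-at-random) errs against doses received by 0.6–1.0 / 0.8–1.4 / 0.7–1.3 points for 300 mg Q16W / 300 mg Q24W / 450 mg Q24W. The SAP rule errs by at most 0.5 / 1.1 / 0.9 (−60% calibration). Dose-aware imputation would rest on about four leavers per arm of 40 at 10%. So the documents do not single out one method.

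A reader might also infer that Protocol 12.2.1, which uses all available values, contradicts a Week 4 start. It leaves further details to the SAP, so the inconsistency lies within SAP 3.4.1.

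**Conclusion.** The point holds and is minor. SAP 3.4.1 gives two incompatible start visits, and uses a separate, unweighted, shorter-span score for participants whose last Lp(a) is before Week 36. That score does not match the stated treatment-policy average for those who leave the study. These conclusions, and the Week 1 weights, need no modelling.

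The sizes rest on assumed profiles and an assumed 10% leaving. The start point moves completers' Week 36 reduction by about 0.4 to 2.5 points. The leaver rule moves an arm mean by about 1 point or less. Against a completer's course, the start point is the larger effect, by about a factor of two or more (−60% calibration: 0.9–2.4 / 0.4–1.6 / 0.7–1.9 against 0.4–1.0 / 0.1–0.6 / 0.3–0.8, arms in the order above).

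A reader might infer that the leaver rule systematically flatters SLN360, for leavers before the second dose or at Week 60. The documents do not support a fixed direction. Under the −60% calibration such leavers do score too favourably at Week 36, but at −70% they range to the other side. The second calibration is at least as credible. At −60%, no 300 mg profile averages beyond −80% over the interval after the second six-monthly dose (−73% to −78%), although Protocol Table 7 has 68.7% of simulated individuals exceeding 80%. At −70% the averages are −79% to −83%. At Week 60, with leaving at Weeks 36 to 48, the 300 mg Q16W shift at −70% also runs from 0.3 too favourable to 0.2 understated. Direction depends on profile, time of leaving and comparator.

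Nor do the documents support a claim that the placebo comparisons are at risk.

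**What to change.** Before unblinding, amend SAP 3.4.1 as follows.

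- State one AUC start visit and apply it to every participant and every formula used.
- Replace the unweighted mean with one pre-specified time-weighted estimator for all participants at Weeks 36, 48 and 60.
- State how the span after the last value is handled, with death addressed separately, so that it matches the stated estimand; or relabel the estimand for study leavers.
- Choose the method and state its assumption. Options include multiple imputation that takes account of doses received, or an MMRM with a trapezoid-weighted combination of visit means. The latter targets the on-dose course and should be described so. Simply cutting the AUC at the last visit leaves the span problem unsolved.
- Keep the current observed-data mean as a sensitivity analysis, and report by arm how many participants have no Lp(a) at or after each endpoint week.

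The cost is SAP wording, modest programming and an explicit missing-data assumption that may rest on few leavers.
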